1.3 Protocol Amendment No. 4 Summary of Changes

This document describes the changes in reference to Protocol Amendment No. 3 dated 18 March 2016.

The primary purpose of this amendment was to add collection of plasma for pharmacokinetic sampling after Day 10, diet requirement update, and independent liver safety review. Full details on changes of text are given in [Appendix F](#) including detailed rationale. The following is a summary of the changes made in the amendment:

- The fat content of the diet of healthy volunteers during their hospital confinement was modified in Section [7.4](#).

Justification: To align the protocol with Ethic Committee's comments.

- The collection of plasma for pharmacokinetic sampling was added in Section [9.1.12.1](#).

Justification: To align the protocol with Ethic Committee's comments.

- The independent liver safety monitoring process was added in Section [11.0](#).

Justification: To align the protocol with Ethic Committee's comments.

TABLE OF CONTENTS

1.0	ADMINISTRATIVE INFORMATION	2
1.1	Contacts	2
1.2	Approval	3
1.3	Protocol Amendment No. 4 Summary of Changes	5
2.0	STUDY SUMMARY	11
3.0	STUDY REFERENCE INFORMATION	14
3.1	Study-Related Responsibilities	14
3.2	Principal Investigator	14
3.3	List of Abbreviations	15
3.4	Corporate Identification	17
4.0	INTRODUCTION	18
4.1	Background	18
4.2	Summary of Nonclinical Data	18
4.3	Summary of Relevant Clinical Studies	19
4.4	Rationale for the Study	20
5.0	STUDY OBJECTIVES AND ENDPOINTS	21
5.1	Objectives	21
5.1.1	Primary Objective	21
5.1.2	Secondary Objectives	21
5.2	Endpoints	21
5.2.1	Primary Endpoints	21
5.2.2	Additional Endpoints	21
5.2.3	Safety Endpoints	22
6.0	STUDY DESIGN AND DESCRIPTION	23
6.1	Study Design	23
6.2	Justification for Study Design, Dose, and Endpoints	24
6.3	Premature Termination or Suspension of Study or Investigational Site	25
6.3.1	Criteria for Premature Termination or Suspension of the Study	25
6.3.2	Criteria for Premature Termination or Suspension of Investigational Site	25
6.3.3	Procedures for Premature Termination or Suspension of the Study or the Participation of Investigational Site	25
7.0	SELECTION AND DISCONTINUATION/WITHDRAWAL OF SUBJECTS	26
7.1	Inclusion Criteria	26
7.2	Exclusion Criteria	26

7.3	Excluded Medications and Dietary Products	28
7.4	Diet, Fluid, and Activity Control, and Subject Housing	28
7.5	Criteria for Discontinuation or Withdrawal of a Subject	29
7.6	Procedures for Discontinuation or Withdrawal of a Subject	30

2.0 STUDY SUMMARY

Name of Sponsor: Takeda Development Center Asia, Pte. Ltd.	Compound: TAK-491			
Title of Protocol: A Randomized, Open-Label and Double-Blind, Placebo-Controlled, Single- and Multiple-Dose, Phase 1 Study of the Pharmacokinetics of TAK-491 40 mg and 80 mg in Healthy Chinese Subjects	IND No.: Not Applicable	EudraCT No.: Not Applicable		
Study Number: TAK-491_112	Phase: 1			
Study Design: This is a randomized, open-label and double-blind, placebo-controlled, single- and multiple-dose, phase 1 study involving 64 healthy Chinese subjects aged 18 to 45 years, inclusive, and considered eligible based on the inclusion and exclusion entry criteria. Subjects will receive TAK-491 or placebo as a single dose followed by multiple doses. Sixteen subjects were allocated equally and randomly to 1 of 2 TAK-491 regimens (40 mg or 80 mg) in the open-label part of the study; the 2 regimens were conducted in parallel.				
Open-Label Part				
Regimen	Regimen Description	Number of Subjects		
A	TAK-491 40 mg as a single dose followed by multiple doses	8		
B	TAK-491 80 mg as a single dose followed by multiple doses	8		
Forty-eight subjects will be allocated equally and randomly to 1 of 3 regimens (TAK-491 40 mg or 80 mg, or placebo) in the double-blind part of the study; the 3 regimens will be conducted in parallel. To maintain the study blind, subjects in this part of the study will receive a least 1 placebo tablet; the TAK-491 40 mg and TAK-491 80 mg tablets differ in size; therefore, placebo tablets for each size will be utilized as appropriate.				
Double-Blind Part				
Regime n	Regimen Description	Number of Subjects		
A	TAK-491 40 mg + placebo as a single dose followed by multiple doses	16		
B	TAK-491 80 mg + placebo as a single dose followed by multiple doses	16		
C	Placebo (2 tablets) as a single dose followed by multiple doses	16		
The pre-dosing study period will consist of a Screening Period (Study Days -28 to -2) and Check-in (Study Day -1). On Day 1, a single dose of TAK-491 or placebo will be administered followed by a pharmacokinetic sampling period through 72 hours postdose (Days 1-4). On Days 4 through 10, subjects will be on a daily dosing regimen, followed by a 24-hour pharmacokinetic assessment period prior to Study Exit (Day 11). The total confinement period for a subject who completes the study will be 12 days. All subjects will return to the site for PK sampling on Days 12-13 and follow-up serum chemistry tests on Day 14. A Follow-up telephone call will be made by the site at 14 (± 2) days following the last dose of study medication (Day 24 [± 2 days]) to inquire for any ongoing adverse events or serious adverse events (SAEs), new adverse events or SAEs, and concomitant medications taken since the final dose of study medication or Early Termination Visit.				

Screening	Check-in	Dosing and PK	72-hr PK	Dosing (a)	Dosing and AM Trough Level (b)	Dosing and 24-hr PK	Study Exit	PK collection	F/U Visit (c)	F/U Call
Days -28 to -2	Day -1	Day 1	Days 2-4	Day 4	Days 5-9	Day 10	Day 11	Days 12-13	Day 14	Day 24 (± 2)

PK=pharmacokinetics.

(a) Dosing will occur after the collection of the 72-hr pharmacokinetic sample.

(b) PK trough samples will be collected on Days 7 to 9.

(c) Serum chemistry testing.

Primary Objective:

To assess the pharmacokinetics of TAK-491 40 mg and 80 mg in healthy Chinese subjects after both single and multiple dose administration.

Secondary Objectives:

To evaluate the safety and tolerability of TAK-491 40 mg and 80 mg in healthy Chinese subjects after both single and multiple dose administration.

Subject Population: Healthy male and female subjects aged 18-45 years, inclusive.

Number of Subjects: Estimated total: 64	Number of Sites: 1 site in China
Dose Levels: TAK-491 40 mg TAK-491 80 mg Matched placebos	Route of Administration: oral
Duration of Treatment: Single dose with sample collection followed with 7 days of daily dosing and sample collection.	Period of Evaluation: Approximately 52 days (including Screening, Day -1 through Study Exit and Follow-up telephone call).
Main Criteria for Inclusion: Healthy male or non-pregnant, non-lactating female subjects of Chinese descent who are 18 to 45 years of age, inclusive, at signing of the informed consent form and first study medication dose. In addition, the subjects must be willing and able to comply with the protocol requirements, must be able to understand and sign a written informed consent form prior to the initiation of any study procedures, have a body mass index between $\geq 19.0 \text{ kg/m}^2$ and $< 24.0 \text{ kg/m}^2$; and must have clinical laboratory results within reference range unless the investigator deems the results not to be clinically significant.	
Main Criteria for Exclusion: The subject has a known hypersensitivity or allergy to any angiotensin type II receptor blocker or to any of the excipients in the TAK-491 formulation to be taken. Subjects will also be excluded if they are unwilling or unable to comply with the protocol or if they use any excluded medications, supplements, or food products outlined in the protocol. The subject has a systolic blood pressure < 110 and $\geq 160 \text{ mm Hg}$ or a diastolic blood pressure of < 60 and $\geq 100 \text{ mm Hg}$. Additionally, subjects will be excluded if they have abnormal Screening or Day -1 laboratory values that suggest a clinically significant underlying disease or have the following laboratory abnormalities: alanine aminotransferase (ALT) and/or aspartate aminotransferase (AST) that exceeds $> 1.5 \times$ the upper limit of normal, hemoglobin value $< 12 \text{ g/dL}$, or who has positive anti-HIV, anti-HCV, or positive HBsAg test results at Screening.	

Main Criteria for Evaluation and Analyses:

Pharmacokinetics:

Plasma pharmacokinetic parameters to be calculated for TAK-536 (the active moiety): area under the concentration-time curve from time 0 to 24 hours (AUC_{24}), area under the concentration-time curve from time 0 to the last quantifiable concentration (AUC_{last}) (after single dose only), area under the concentration-time curve from time 0 to infinity (AUC_{∞}) (after single dose only), average concentration during a dosing interval, at steady state ($C_{av,ss}$) (after multiple dose only), maximum observed concentration (C_{max}), minimum observed concentration during a dosing interval (C_{min}) (after multiple dose only), observed concentration at the end of a dosing interval (C_{trough}) (after multiple dose only), apparent clearance after extravascular administration (CL/F) (after single dose only), terminal disposition phase rate constant (λ_z) (after single dose only), terminal disposition phase half-life ($t_{1/2z}$) (after single dose only), time of first occurrence of C_{max} (t_{max}), and apparent volume of distribution during the terminal disposition phase after extravascular administration (V_z/F) (after single dose only).

Urine pharmacokinetic parameters to be calculated for TAK-536: amount of drug excreted in urine (Ae_{24} , Ae_{72} [after single dose only], Ae_{0-2} , Ae_{2-4} , Ae_{4-8} , Ae_{8-12} , Ae_{12-24} , Ae_{24-48} [after single dose only], Ae_{48-72} [after single dose only]), renal clearance (CL_R), and fraction of administered dose of drug excreted in urine during a dosing interval (f_{e24} and f_{e72}) (f_{e72} after single dose only).

Safety and Tolerability:

Safety and tolerability assessment will include physical examination findings, vital signs, 12-lead electrocardiogram (ECG) results, laboratory evaluations (hematology, serum chemistry, and urinalysis), and adverse events (AEs).

Statistical Considerations:

Pharmacokinetic Measures:

Concentrations of TAK-536 in plasma will be summarized by regimen over each scheduled sampling time using descriptive statistics for the open-label and double-blind parts separately and overall.

The amount of TAK-536 excreted in urine will be summarized by regimen over each scheduled sampling interval using descriptive statistics for each part separately and overall.

Plasma and urine PK parameters of TAK-536 will be summarized by regimen using descriptive statistics for each part separately and overall.

Safety:

AEs will be presented in the listings, and TEAEs will be summarized. Clinical laboratory variables, vital sign, and ECG parameters will be summarized with descriptive statistics for Baseline, postdose, and change from Baseline to postdose values. The percentage of subjects with at least 1 postdose laboratory variable, vital sign, and ECG parameter that meet Takeda's predefined criteria will be summarized. Physical examination findings will be presented in the data listings. All summaries will be performed by regimen for each part separately and overall.

Sample Size Justification:

A total sample size of 64 subjects will be enrolled in this study. Sixteen subjects, 8 per regimen (TAK-491 40 mg and 80 mg) were randomized to the open-label part of the study. Forty-eight subjects, 16 per regimen (TAK-491 40 mg, 80 mg, and placebo) will be randomized to the double-blind part of the study. The sample size is considered sufficient for evaluation of safety, tolerability, and PK of each part of the study, and was not based on statistical power considerations.

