7.1 Inclusion Criteria

Subject eligibility is determined according to the following criteria:

1. In the opinion of the investigator, the subject is capable of understanding and complying with protocol requirements.
2. The subject or, when applicable, the subject's legally acceptable representative signs and dates a written, informed consent form and any required privacy authorization prior to the initiation of any study procedures.
3. The subject is a healthy adult male or female subject of Chinese descent.
4. The subject is aged 18 to 45 years, inclusive, at the time of informed consent and first study medication dose.
5. The subject has a body mass index (BMI) $\geq 19.0 \text{ kg/m}^2$ and $< 24.0 \text{ kg/m}^2$, at Screening.
6. The subject has clinical laboratory evaluations (including clinical chemistry [fasted for at least 8 hours for the screening assessment], hematology, and complete urinalysis) within the reference range for the testing laboratory, unless the results were deemed by the investigator to be not clinically significant at Screening and Check-in (Day -1).
7. The subject is willing to refrain from strenuous exercise, from 72 hours before Check-in (Day-1) until after Final Visit.
8. A female subject of childbearing potential* who is sexually active with a nonsterilized* male partner agrees to use routinely adequate contraception* from signing of informed consent throughout the duration of the study and for 30 days after the last dose of study drug.

*Definitions and acceptable methods of contraception are defined in Section 9.1.9
Contraception and Pregnancy Avoidance Procedure and reporting responsibilities are defined in Section 9.1.10 Pregnancy.

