12. Subject has positive test result for anti-HIV, anti-HCV antibodies, or for HBsAg at Screening.
13. Subject has used nicotine-containing products (including but not limited to cigarettes, pipes, cigars, chewing tobacco, nicotine patch or nicotine gum) within 28 days prior to Check-in (Day -1). Cotinine test is positive at Screening or Check-in (Day -1).
14. The subject has poor peripheral venous access.
15. Subject has donated or lost 450 mL or more of his or her blood volume (including plasmapheresis), or had a transfusion of any blood product within 30 days prior to Day 1.
16. Subject has a Screening or Check-in (Day -1) abnormal (clinically significant) ECG. Entry of any subject with an abnormal (not clinically significant) ECG must be approved, and documented by signature by the principal investigator.
17. Subject has abnormal Screening or Check-in (Day -1) laboratory values that suggest a clinically significant underlying disease or subject with the following laboratory

abnormalities: alanine aminotransferase (ALT) and/or aspartate aminotransferase (AST) $>1.5\times$ the upper limit of normal.

18. Subject has a hemoglobin value <12 g/dL at Screening.

19. The subject has a systolic blood pressure <110 and ≥160 mm Hg or a diastolic blood pressure <60 and ≥100 mm Hg at Screening or Check-in (Day -1).

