7.11.1 Adverse Events

Pretreatment events (PTEs) and AEs will be coded using MedDRA Version 19.0 or higher.

A PTE is defined as any untoward medical occurrence in a clinical investigation subject who has signed informed consent to participate in a study, but prior to administration of any study medication; it does not necessarily have to have a causal relationship with study participation.

An AE is defined as any untoward medical occurrence in a clinical investigation subject administered a pharmaceutical product, including placebo; it does not necessarily have to have a causal relationship with this regimen.

Treatment-emergent adverse events (TEAE) are defined as any AEs, regardless of relationship to study drug, which occurred or worsened in severity on or after the first dose of study medication and until 30 days after the last dose of study medication is received.

When calculating the frequency and percentage of subjects who reported TEAEs, a subject will be counted only once for each SOC or PT when multiple TEAEs are coded to the same SOC or PT. Thus, if a subject has two distinct AEs, each of which corresponds to a distinct PT but both of which correspond to the same SOC, then that subject will be counted once at that SOC subject-count summary level and once at each of the two PTs subject-count summary levels. For the intensity summaries, if a subject reports multiple TEAE coded to the same SOC or PT, the TEAE with maximum intensity will be included in the summary. For the relationship summaries, if a subject reports multiple TEAEs coded to the same SOC or PT, the TEAE most related to study drug will be included in the summary.

Adverse events will be summarized by study part, regimen and TAK-491 overall for double blind part, which will include the number and percentage of subjects as follows:

- Overview of Treatment-Emergent Adverse Events
- Treatment-Emergent Adverse Events by System Organ Class and Preferred Term
- Subject Mappings for Treatment-Emergent Adverse Events
- Treatment-Emergent Adverse Events by Preferred Term
- Non-Serious Treatment-Emergent Adverse Events by and Preferred Term
- Relationship of Treatment-Emergent Adverse Events by System Organ Class and Preferred Term
- Drug-Related Treatment-Emergent Adverse Events by System Organ Class and Preferred Term

- Intensity of Treatment-Emergent Adverse Events by System Organ Class and Preferred Term

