7.11.2 Clinical Laboratory Evaluations

Clinical laboratory tests will be evaluated by central laboratory and presented using the International System of Units (SI) units unless otherwise stated. [Table 4.c](#) shows the scheduled measurements for clinical laboratory tests and [Table 7.d](#) shows a list of all clinical laboratory tests.

Table 7.d Clinical Laboratory Tests

Hematology	Serum Chemistry	Urinalysis
Red blood cells	Alanine aminotransferase	pH
White blood cells with differential (neutrophils, eosinophils, basophils, lymphocytes, monocytes)	Albumin	Specific gravity
Hemoglobin	Alkaline phosphatase	Protein
Hematocrit	Aspartate aminotransferase	Glucose
Platelets	Total bilirubin	Blood
	Total protein	Ketones
	Creatinine	Microscopic Analysis (a):
	Blood urea nitrogen	RBC/high power field
	Creatine kinase	WBC/high power field
	γ -Glutamyl transferase	Epithelial cells, casts etc.
	Potassium	
	Sodium	
	Glucose	
	Chloride	
	Triglycerides	
	HDL-C	
	LDL-C	
	Total cholesterol	
Diagnostic Screening:		
Serum	Urine	Breath
HBsAg, anti-HCV, anti-HIV (b) Additional Virology Tests: Anti-HBsAb, HBeAg, anti-HBeAb, anti-HBcAb, EBV VCA IgG, EBV VCA IgM, Anti-CMV IgG, and Anti-CMV IgM (c)	Drug screen, including amphetamines, barbiturates, benzodiazepines, cannabinoids, cocaine, opiates, and cotinine	Breath alcohol test
Female Subjects only:		
Serum hCG at Screening, Check-in, and Study Exit or Early Termination		

EBV= Epstein-Barr virus viral capsid antigen, hCG=human chorionic gonadotropin, RBC=red blood cell, WBC=white blood cell.

(a) Microscopic analysis should be performed only if urine evaluations are abnormal.

(b) HBsAg, anti-HCV, and anti-HIV test results will be collected for all subjects.

(c) The results for the additional virology tests performed at Screening will be recorded in the (e)CRF for randomized subjects only.

The following summaries will be provided for laboratory data by part and regimen:

- Baseline, postdose, and, change from baseline to postdose values for quantitative measurements.
- Number and percent of urine parameters results for categorical measurements.
- Number and percent of subjects with markedly abnormal value (MAV) which identified by the criteria in [Appendix A](#).
- Shift from baseline of high/low/normal values according to normal range criteria (baseline versus each post-baseline visit).

If a subject has multiple values within a particular visit window, the most abnormal result will be used for summary.

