7.11.3 Vital Signs

Vital signs' (including pulse rate, weight, SBP, DBP, body temperature and respiratory rate) collection schedule is presented in [Table 4.c](#), and baseline, postdose, and changes from baseline to each post-dose values will be summarized using descriptive statistics by visit and regimen for each part.

Number and percentage of subjects with markedly abnormal value (MAV) will also be tabulated based on the criteria listed in [Appendix B](#).

All vital signs data will be presented in the listings.

7.11.4 12-Lead ECGs

ECG data collection schedule is presented in [Table 4.c](#). and will be summarized with descriptive statistics by regimen for baseline, postdose and change from baseline to postdose value for each part.

Overall ECG interpretation category (within normal limits, not clinically significant abnormal, clinically significant abnormal) is collected by eCRF according to the scheduled measurements. Shifts in ECG interpretation will be presented as cross-tabulations of numbers of subjects with normal, not clinically significant abnormal, and clinically significant abnormal ECG interpretation results and will include categories for missing and totals.

ECG parameters with markedly abnormal value (MAV) will be tabulated based on the value categories listed in [Appendix C](#).

Summary of Subjects with QTcF in various pre-defined categories will also be tabulated. Categories are listed in [Appendix C](#).

ECG data will be presented in the subject data listings.

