Appendix C Criteria for Out-of-Range Values for the 12-Lead ECG Parameters

Parameter	Lower Criteria	Upper Criteria
Heart rate	<50 beats per minute	>120 beats per minute
QT Interval	\leq 50 milliseconds	\geq 460 milliseconds
QTcF Interval	\leq 50 milliseconds	\geq 500 milliseconds OR \geq 30 milliseconds change from baseline and \geq 450 milliseconds

QTcF interval in pre-defined various criteria categories:

- Increase from baseline \geq 30 msec
- Increase from baseline \geq 60 msec
- $>$ 500 msec
- $>$ 500 msec and increase from baseline \geq 60 msec

ELECTRONIC SIGNATURES

Signed by	Meaning of Signature	Server Date (dd-MMM-yyyy HH:mm 'UTC')
PPD	Statistical Approval	01-May-2017 16:28 UTC
	Pharmacovigilance Approval	01-May-2017 18:16 UTC
	Clinical Science Approval	01-May-2017 19:10 UTC
	Statistical Approval	01-May-2017 20:14 UTC
	Clinical Pharmacology Approval	02-May-2017 01:15 UTC

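### The markedly-abnormal-value tables do not separate new from pre-existing findings for pulse, heart rate, temperature, QT, creatine kinase and urinalysis

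*Protocol*

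**What the plan says.** **Counting rule.** Protocol 2.0 (Statistical Considerations, Safety): "The percentage of subjects with at least 1 postdose laboratory variable, vital sign, and ECG parameter that meet Takeda's predefined criteria will be summarized". Protocol 13.1.4 repeats the intention to identify values meeting the sponsor's criteria and adds no baseline condition.

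**SAP.** For laboratory data (7.11.2): "Number and percent of subjects with markedly abnormal value (MAV) which identified by the criteria in" Appendix A. For vital signs (7.11.3): "Number and percentage of subjects with markedly abnormal value (MAV) will also be tabulated based on the criteria listed in" Appendix B. For ECG (7.11.4): "ECG parameters with markedly abnormal value (MAV) will be tabulated based on the value categories listed in" Appendix C. None of the three mentions pre-dose status.

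**Contrast with adverse events.** SAP 7.11.1 limits treatment-emergent events to those "which occurred or worsened in severity on or after the first dose of study medication".

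**Entry.** Out-of-range laboratory results are allowed "unless the results were deemed by the investigator to be not clinically significant at Screening and Check-in (Day -1" (Protocol 7.1, No. 6). For ECGs, exclusion No. 16 in Protocol 7.2 says: "Entry of any subject with an abnormal (not clinically significant) ECG must be approved". Numeric limits exist for ALT/AST, hemoglobin and blood pressure. There are none for pulse, heart rate, temperature, QT, creatine kinase or urinalysis.

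**Baseline.** SAP 7.1.3 uses the last value before the first dose.

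**The concern.** Most limits in SAP Appendices A to C are absolute or are multiples of the normal range: pulse or heart rate below 50, temperature below 35.6 or above 37.7 °C, QT at or above 460 ms, creatine kinase above 5 × ULN, urine protein, glucose or blood at 1+ or more. A subject can sit beyond several of these before any drug is given and still be eligible. The table will then show a post-dose MAV. That is literally true, but it is easily read as something that arose on treatment.

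Safety and tolerability is the secondary objective. The double-blind part was added to separate drug effects from other causes (Protocol 6.2), so a count that mixes new and pre-existing findings works against that purpose. The open-label arms have no placebo column to show the background. In the double-blind part, chance imbalance in pre-existing findings between arms of 16 would appear as a difference in post-dose abnormality.

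**Working it through.** The plan gives no figure on this point to reproduce. The check has two steps.

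**Step 1. Which parameters are exposed?** Compare the entry limits (Protocol 7.1, 7.2) with the MAV limits (SAP Appendices A to C).

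| Parameter | Entry limit | MAV limit | MAV possible at Screening or Day -1? |
|---|---|---|---|
| ALT, AST | excluded if > 1.5 × ULN | > 3 × ULN | No |
| Systolic BP | excluded if < 110 or ≥ 160 | < 85 or > 180 | No |
| Diastolic BP | excluded if < 60 or ≥ 100 | < 50 or > 110 | No |
| Pulse, heart rate | none | < 50 or > 120 | Yes |
| Temperature | none | < 35.6 or > 37.7 °C | Yes |
| QT | judgement only | ≥ 460 ms (upper) | Yes |
| Creatine kinase | judgement only | > 5 × ULN | Yes |
| Urinalysis | judgement only | e.g. protein ≥ 1+ | Yes |

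Two criteria differ in form. One QTcF branch requires at least "30 milliseconds change from baseline" together with a value of 450 ms or more, so it already refers to baseline. Urine red cells need two values within 30 days of one another, but nothing says that both must be post-dose.

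**Step 2. How large could the effect be?** Arm sizes are 8 (open-label) and 16 (double-blind), from Protocol 13.3.

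*One subject:* 100/8 = 12.5 points; 100/16 = 6.25 points.

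*Chance that an arm contains at least one subject already beyond a given limit:* 1 − (1 − p)^n. The prevalence p is an assumption, because the documents give none.

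| p | n = 8 | n = 16 | Two arms of 16 differ by ≥ 2 such subjects |
|---|---|---|---|
| 2% | 15% | 28% | 6% |
| 5% | 34% | 56% | 20% |
| 10% | 57% | 81% | 36% |

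The last column sums the product of two independent binomial(16, p) distributions over all pairs of counts that are at least 2 apart.

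*Pulse illustration, no drug effect.* The schedule gives 3 pre-dose readings (Screening, Day -1, Day 1) and 12 later ones (Days 2 to 13). Assumed: population mean 62–70 bpm, between-subject SD 7–9, within-subject SD 4–5, readings in whole beats. For a subject with true mean M, one reading is below 50 with probability q = Φ((49.5 − M)/SD within). Averaging over M:

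- any post-dose reading < 50: E[1 − (1 − q)^12];
- share of those with any pre-dose reading < 50: E[(1 − (1 − q)^12)(1 − (1 − q)^3)] / E[1 − (1 − q)^12];
- share of those below 50 at the SAP baseline (normally the Day 1 reading): the same ratio with q in place of 1 − (1 − q)^3.

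Simulating 400,000 subjects at each of the eight corners of these ranges gives 3–32% for the first quantity, 27–59% for the second and 12–37% for the third. Without rounding to whole beats, the upper ends rise only to 34%, 60% and 38%.

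**The case against.** The strongest reply is that this is a small presentation gap in a descriptive study, and much of that reply stands.

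- **The main safety signals are clean.** A reader might infer that the ALT/AST or blood pressure counts are contaminated. They are not: Step 1 shows that no eligible subject can meet those MAV limits at Screening or Day -1. In principle a Day 1 pre-dose blood pressure could still do so.
- **Not every criterion is one value against a fixed limit.** The QTcF change branch and the repeated urine red cell rule are exceptions.
- **Other outputs help.** A reader might infer that heart rate and QT have no categorical shift output of any kind. SAP 7.11.4 does plan a shift table of overall ECG interpretation, and SAP 7.11.2 plans laboratory shifts by normal range. Change from baseline is summarized and all values are listed. But neither shift table uses the MAV limits, and pulse and temperature have no categorical shift at all.
- **Sponsor guidance is unseen.** The SAP's references include sponsor guidance on markedly abnormal values and on data handling, which might set a baseline rule. The protocol sentence nevertheless reads as a complete counting rule, and nothing in the SAP text qualifies it.
- **Much of the no-drug-effect count is not pre-existing.** With 63–88% of the pulse counts in the illustration not below 50 at baseline (100 minus 37 and 12), repeated reading against a fixed limit accounts for most of them. A treatment-emergent count does not remove that part; comparison with placebo does, in the double-blind part only.

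**Conclusion.** The point holds for pulse and heart rate, temperature, QT, creatine kinase and urinalysis: as written, a subject beyond one of these limits both before and after dosing is counted, and no planned output separates new from pre-existing MAVs by the MAV limit. It does not hold for ALT, AST, blood pressure or the QTcF change-from-baseline branch.

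The 12.5 and 6.25 points per subject follow from the arm sizes alone. The arm-level probabilities and the pulse ranges rest on assumed prevalences and an assumed pulse distribution; they show scale and do not predict this trial's results. A reader might go further and conclude that the safety tables will mislead about drug effect. The documents do not support that: no formal tests are planned, the liver counts are unaffected, and pre-existing cases can be traced in the listings of 64 subjects. This is a minor improvement to a secondary safety output, and the primary PK endpoints are not involved.

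**What to change.** In SAP 7.11.2 to 7.11.4, with matching wording in Protocol 2.0 and 13.1.4:

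1. Keep the present count of subjects with at least one post-dose MAV, so that worsening of an already abnormal value is not lost. Write the post-dose restriction into the SAP, whose MAV sentences omit it.
2. Beside it, add a treatment-emergent count: subjects with a post-dose MAV among those who did not meet the same limit at the baseline defined in SAP 7.1.3, with that group as denominator. A cross-tabulation of baseline by post-dose MAV status, per parameter and regimen, would serve equally well.
3. Optionally, add a sensitivity version that excludes subjects who met the limit at any pre-dose reading.
4. For urine red cells, state whether a pre-dose value may form one of the required pair.

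The cost is SAP wording, one derived flag and an extra column, all from data already collected. Denominators will vary slightly by parameter, which needs a footnote in arms of 8 and 16.
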